3 SAMPLE SIZE

This sample size is not based on statistical power calculation. The sample size is expected to provide adequate information to determine the optimal dose of ASP5354 for ureter visualization.

Up to 15 subjects will be randomly assigned at each dose level. This results in a total expected sample size of a maximum of 45 subjects. In case, additional dose groups are added, sample size can increase to a maximum of 90 subjects (15 subjects in each of the six possible doses).

4 ANALYSIS SETS

In accordance with International Conference on Harmonization (ICH) recommendations in guidelines E3 and E9, the following analysis sets will be used for the analyses.

The determination of whether subjects are included or excluded from the analysis sets except pharmacokinetic analysis set (PKAS) will be made prior to database hard-lock.

4.1 Full Analysis Set

The full analysis set (FAS) will consist of all subjects who receive ASP5354 and have at least 1 assessment of ureter visualization during surgery. This will be the primary analysis set for efficacy analyses.

4.2 Safety Analysis Set

The safety analysis set (SAF) consists of all subjects who receive ASP5354. The SAF will be used for all summaries of the safety data, unless otherwise specified.

4.3 Pharmacokinetic Analysis Set

The PKAS consists of all subjects who receive ASP5354 for which at least 1 plasma or urine concentration data are available with the time of dosing and sampling. Inclusion of subjects in the PKAS with important protocol deviations will be considered by the pharmacokineticist on a case-by-case basis.

The PKAS will be used for all summaries of the pharmacokinetic data.

5 ANALYSIS ENDPOINTS

5.1 **Primary Efficacy Endpoint**

The primary endpoint is the anatomical visualization of the index ureter(s) 30 minutes after dosing of ASP5354 and the end of surgery.

The incidence of anatomical visualization of ureter(s) will be assessed at approximately 10, 20, 30, 45 and 60 minutes postadministration of ASP5354, and then every 30 minutes thereafter and/or at the last time point before removal of visualization instruments (end of surgery) by the investigator intraoperatively using a binary "Yes" or "No" question on the ability to visualize the ureter: "Can the ureter be adequately visualized with near-infrared fluorescence (NIR-F)?"

- If the answer to the question 30 minutes after ASP5354 administration and at the end of surgery is equal to "Yes", then anatomical visualization of the index ureter(s) was a success.
- All other cases will be handled as "Not a success".

If both ureters are index per investigator, both need to have successful visualization for a subject to have successful visualization.

In the case that if the anatomical visualization of the index ureter(s) was not assessed at 30 minutes after ASP5354 administration, the answer will be imputed as follows:

- If the answer at the nearest time points before and after 30 minutes both = Yes, then the answer to the question 30 minutes after ASP5354 administration will be imputed as = Yes.
- If the answer at the nearest time points before and after 30 minutes both = No, then the answer to the question 30 minutes after ASP5354 administration will be imputed as = No.
- All other cases will be handled as "Not Done" at 30 minutes after ASP5354 administration, and imputing will not occur.

5.2 Secondary Efficacy Endpoints

Since no efficacy endpoint is specified as secondary endpoint, it is not applicable.

5.3 Exploratory Efficacy Endpoints

Exploratory efficacy endpoints are the following:

- The Likert Scale for qualitative response about the intensity of fluorescence at the predefined time points during surgery
- Duration of anatomical visualization of the index ureter(s) from the first time of positive visualization to the last time point of positive visualization
- Signal background ratio (SBR)
- Binary questions (Yes/No) for the benefit of ASP5354
- Ability to visualize the contralateral ureter when amenable to visualization

5.4 Safety Endpoints

Safety and tolerability endpoints include adverse events (AEs), laboratory test results, vital signs, electrocardiograms (ECGs) and findings in physical examination.

5.4.1 Adverse Event

AE will be assessed by evaluation of the following variables:

- Treatment-emergent adverse events (TEAEs; frequency, severity, seriousness, and relationship to study drug)
 - TEAE is defined as an AE observed after ASP5354 administration and up to the follow-up period (up to Day 10).
 - If the AE occurs on Day 1 and the onset check box is marked "Onset after first study drug taken" or the both onset check boxes "Onset before first study drug taken" and "Onset after first study drug taken" are marked or left blank, then the AE will be considered treatment emergent.
 - If the AE occurs on Day 1 and the onset check box is marked "Onset before first study drug taken", then the AE will not be considered treatment emergent.
 - If a subject experiences an event both during the pre-investigational period and during the investigational period, the event will be considered as TEAE only if it is reported with a new start date (i.e., as a new AE).
 - Any AEs with onset dates completely missing will be considered TEAEs in summaries unless the investigator has noted on the CRF the event began prior to treatment. AEs with partially missing onset dates will be assumed TEAEs unless the available portion of the date indicates that the onset was strictly before start of study medication.
 - A drug-related TEAE is defined as any TEAE with possible relationship to study treatment as assessed by the investigator or with missing assessment of the causal relationship.

• Serious adverse events (SAEs) include adverse events that are flagged as serious by the investigator on eCRF, or upgraded by the Sponsor based on review of the Sponsor's list of Always Serious terms.

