7.3.1 Time Period for Collecting Adverse Event and Serious Adverse Event Information

In order to identify any events that may be associated with study procedures and could lead to a change in the conduct of the study, Astellas collects AEs even if the subject has not received IP. AE collection begins after the signing of the ICF and will be collected through to the last clinical study protocol-defined assessment or when the subject is determined to be a screen failure.

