7.3.2 Method of Detecting Adverse Events and Serious Adverse Events

The methods of recording, evaluating and assessing seriousness, causality and severity of AEs and SAEs are described in [Appendix 12.4 Adverse Events: Definitions and Procedures for Recording, Evaluating, Follow-up or Reporting]. Care will be taken not to introduce bias when detecting AEs and/or SAEs. Open-ended and nonleading verbal questioning of the subject is the preferred method to inquire about AE occurrences.

An AE with a change in severity is recorded as a new AE.

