9.5.1 Adverse Events

AEs will be coded using MedDRA and graded using the National Cancer Institute-common terminology criteria for AE (NCI-CTCAE, version 5.0).

A TEAE is defined as an AE observed after administration of the IP and up to the follow-up period. An IP-related TEAE is defined as any TEAE with a causal relationship assessed as “yes” by the investigator.

The number and percentage of subjects with TEAEs, IP-related TEAEs, serious TEAEs, IP-related serious TEAEs will be summarized by SOC, PT and dose group. The number and percentage of TEAEs by toxicity grade will also be summarized. The worst toxicity grade will be summarized if the same AE is recorded more than once for a subject.

AE data will be listed.

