12.4.1 Definition of Adverse Events

An AE is any untoward medical occurrence in a subject administered an IP, and which does not necessarily have to have a causal relationship with this treatment. An AE can therefore be any unfavorable and unintended sign (including an abnormal laboratory finding), symptom, or disease (new or exacerbated) temporally associated with the use of IP whether or not considered related to the IP.

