12.4.4 Criteria for Defining the Severity of an Adverse Event

AEs, including abnormal clinical laboratory values, will be graded using NCI-CTCAE guidelines (version 5.0). The items that are not stipulated in the NCI-CTCAE version 5.0 will be assessed according to the criteria below and entered into the eCRF:

Table 7 Grading Scale Defining the Severity of an Adverse Event

Grade	Assessment Standard
1 - Mild	Asymptomatic or mild symptoms, clinical or diagnostic observations only; intervention not indicated
2 - Moderate	Minimal local or noninvasive intervention indicated; limiting age-appropriate instrumental ADL ^a
3 - Severe	Medically significant but not immediately life-threatening, hospitalization or prolonged hospitalization indicated; disabling; limiting self-care ADL ^b
4 - Life-threatening	Life-threatening consequences, urgent intervention indicated
5 - Death	Death related to AE

ADL: activities of daily living; AE: adverse event

a Instrumental ADL refer to preparing meals, shopping for groceries or clothes, using the telephone, managing money, etc.

b Self-care ADL refer to bathing, dressing and undressing, feeding self, using the toilet, taking medications and not bedridden.

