6.5.1 Adverse Events

AEs will be coded using MedDRA and graded using the National Cancer Institute-common terminology criteria for AE (NCI-CTCAE, version 5.0).

A TEAE is defined as an AE observed after administration of the IP and up to the follow-up period. An drug-related TEAE is defined as any TEAE with a causal relationship assessed as "yes" by the investigator.

An overview summary table will include number and percentages of subjects with TEAEs, drug-related TEAEs, serious TEAEs, drug-related serious TEAEs, TEAEs leading to death, drug-related TEAEs leading to death and of all deaths. Frequencies and percentages of TEAEs and drug-related TEAEs by worst NCI CTCAE will be presented in the overview, too.

The number and percentage of subjects with TEAEs, drug-related TEAEs, serious TEAEs, drug-related serious TEAEs will be summarized by SOC and PT. The number and percentage of TEAEs by NCI CTCAE grade will also be summarized. The worst toxicity grade will be summarized if the same AE is recorded more than once for a subject.

All AE data will be listed.

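### An adverse event that began before dosing and improved by a grade afterwards can be counted as treatment-emergent, because no rule compares the new record with the pre-dose grade

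*SAP*

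**What the plan says.** Four rules bear on this point.

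- **Collection.** Protocol 7.3.1: "AE collection begins after the signing of the ICF". Screening can start 28 days before the operation, and ASP5354 is given during the operation, so an AE can already be open at dosing.
- **Recording.** Protocol 7.3.2: "An AE with a change in severity is recorded as a new AE". The sentence does not separate worsening from improvement.
- **Classification.** SAP 5.4.1 gives the general rule, "TEAE is defined as an AE observed after ASP5354 administration and up to the follow-up period (up to Day 10", and Protocol 9.5.1 agrees: "A TEAE is defined as an AE observed after administration of the IP and up to the follow-up period". For an event seen in both periods, SAP 5.4.1 adds that "the event will be considered as TEAE only if it is reported with a new start date (i.e., as a new AE". For Day 1 events it uses an onset check box. A record marked only as starting before study drug is not a TEAE. A record marked as starting after it, or with both boxes marked or both blank, is a TEAE.
- **Tabulation.** SAP 6.5.1 counts subjects with TEAEs by system organ class and preferred term, and for grades says "The worst toxicity grade will be summarized if the same AE is recorded more than once for a subject".

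**The concern.** A treatment-emergent event should be one that appears or gets worse after treatment. Here the deciding question is whether a new record exists, and the protocol creates one for improvement as well as for deterioration. An event that was there before ASP5354 and is subsiding could therefore be tabulated as if it had emerged after the drug.

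Safety and tolerability form a secondary objective. There is no placebo arm against which such events could be compared, and each dose level has at most 15 subjects. One misclassified subject is therefore visible in a row of a by-dose table. Because dosing takes place during surgery, events from the preoperative period or the early part of the operation are the natural candidates.

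**Working it through.** The plan states no figure that depends on this point, so the check is to follow one event through the rules.

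**Step 1: recording.** Take an AE that is grade 2 before dosing and grade 1 after it. Its severity has changed, so Protocol 7.3.2 makes the grade 1 episode a new AE.

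**Step 2: start date.** Protocol 7.3.2 does not mention start dates. SAP 5.4.1 treats a new start date and a new AE as the same thing. The inference is that the grade 1 record starts when the grade changed, which is after dosing.

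**Step 3: classification.** The words 'only if' in SAP 5.4.1 state a necessary condition, which the record meets. Sufficiency comes from the general definition, which needs only an AE observed after dosing. No text in Protocol 9.5.1, SAP 5.4.1 or SAP 6.5.1 asks for a grade above the pre-dose grade. The record is a TEAE.

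**Step 4: Day 1.** If the grade changes on Day 1, the check box decides. Completed for the new record, it says onset after study drug, and the result is a TEAE. Completed for the original event, it says onset before, and the result is not a TEAE. The documents do not say which is meant. The box rule covers only AEs occurring on Day 1, so it does not reach a step-down record dated later.

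**Step 5: tabulation.** The worst-grade rule chooses among repeated records. It does not remove a subject whose only post-dose record is an improvement.

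The cases side by side, assuming that the new record carries a post-dose start date and, on Day 1, that the box is completed for that record:

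| Before dosing | After dosing | As written | Worsening-or-recurrence rule |
|---|---|---|---|
| Grade 3 | Grade 2 | TEAE | Not a TEAE |
| Grade 2 | Grade 1 | TEAE | Not a TEAE |
| Grade 1 | Grade 2 | TEAE | TEAE |
| Resolved | Recurs | TEAE | TEAE |
| Grade 2 | Grade 2, no new record | Not a TEAE | Not a TEAE |

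The two approaches differ only in the first two rows.

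**Size of one misclassification.** The change in a preferred-term row is 1/n.

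- Full dose group (SAP 3, up to 15 per dose level): 1/15 = 6.7 percentage points.
- Group stopped after the first review of 3 subjects (Protocol 4.1): 1/3 = 33.3 percentage points.

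These are upper limits. The row does not change if the subject already has a genuine TEAE under the same term, and the any-TEAE row does not change if the subject has any other TEAE.

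**Number expected.** This would be n × P(AE open at dosing) × P(a lower-grade record after dosing). The documents give neither probability, so the product cannot be evaluated.

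**The case against.** The strongest reply is that the chain is partly inferred. Protocol 7.3.2 is silent on start dates, and Protocol 12.2.3 leaves data-entry detail to the eCRF instructions, which are not part of these documents. Those instructions might carry the original onset date forward. This stands, and it is why the conclusion is that such an event can be counted, not that it always will be.

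Second, a TEAE must first be an AE, and Protocol 12.4.1 speaks of "disease (new or exacerbated) temporally associated with the use of IP". A subsiding event is arguably neither. But that definition does not limit the recording rule in 7.3.2, and the SAP's TEAE rule does not refer to it. The most it shows is an ambiguity, which also needs settling.

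Third, the exposed group is narrow. The AE must begin between consent and dosing, still be open at dosing, and then improve without resolving outright. The error over-counts, which is the same direction as the SAP's other defaults (AEs with an entirely missing onset date are normally counted as TEAEs). All AE records are listed, so the earlier record can be found. These points lower the severity but do not repair the rule.

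A reader might infer more than the documents support:

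- **That the serious and drug-related tables are inflated as well.** A serious row changes only if the step-down record is itself flagged serious. A drug-related row changes only if that record is assessed as related, or has missing causality, which SAP 5.4.1 treats as related.
- **That most dose groups will contain such a case.** Any probability of this kind would only restate assumed inputs, since the documents offer nothing to anchor them.
- **That dose selection is distorted.** Protocol 4.1 has the review committee assess visualization data and names ureter visualization and fluorescence intensity as criteria. Although it allows the totality of data, it does not name TEAE rates. No hypothesis is tested on safety.

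**Conclusion.** The point holds in a limited form. The recording rule ignores the direction of a severity change, and the TEAE rule makes no grade comparison, so an AE that began between consent and dosing and improved by a grade afterwards can be counted as a TEAE. This rests on one inference, that the new record carries a new start date. For Day 1 records it also depends on an unstated convention for the check box.

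The effect per subject is up to 6.7 percentage points in a preferred-term row at n=15 and up to 33.3 points at n=3. The number of subjects affected is unknown. The primary endpoint is untouched. Severity is minor to moderate: this is more than a missing detail, because a stated rule can give the wrong classification, but it concerns few records and the listings would show them.

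**What to change.** In SAP 5.4.1, replace the new-start-date condition with a rule to this effect: a post-dose record of an event already present before ASP5354 counts as a TEAE only if (a) its NCI-CTCAE grade exceeds the last pre-dose grade, (b) it becomes serious after dosing, or (c) the event had resolved before dosing and recurred. Records of equal or lower grade are listed but not counted. Apply the same rule to Day 1 records marked as onset after study drug, so that the result no longer depends on how the box was completed. SAP 6.5.1 should point to this rule, because it repeats the general definition without it.

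The cost is a short SAP revision and a programming step that compares grades. The documents do not say that AE records are linked, so records of the same event would have to be joined by preferred term and contiguous dates, with manual review where dates are partial. In a study of at most 90 subjects this is manageable. True worsening is still counted, and no safety record leaves the listings.

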6.10.2 Imputation Rules for Incomplete Dates

In case of missing partial start and stop dates for concomitant medications, the following rules will be used:

If the start date is missing or partial:

- if the month is missing, use January
- if the day is missing, use the first day of the month under consideration
- if the year is missing, use year of the informed consent date
- if the entire date is missing then:
 - a) If the concomitant medication did not start more than 28 days prior to treatment administration (operation day), use the informed consent date.
 - b) Otherwise, use the 29th day prior to treatment administration.

If the stop date is missing or partial and the concomitant medication is not ongoing then:

- if the month is missing, use December
- if the day is missing, use the last day of the month under consideration
- if the year or the entire date is missing, set the stop date to December 31st, 2099

If the imputed start date is after the stop date, then the imputed start date will be 1 day prior to the stop date.

For AEs, a missing or incomplete onset date will be imputed according to the following conventions.

If only the year is known for the AE onset date, the imputed onset date will be the latest of the following non-missing dates:

- Date of first dose of study drug
- January 1 of the year of AE onset date

If only the month and year is known for the onset date, set the surrogate onset date to the first day of that month and then apply the following rules.

- If the month and year of the onset date is prior to the month and year of the first dose of study drug, then the surrogate onset date will be the imputed onset date.
- If the month and year of the onset date is on or after the month and year of the first dose of study drug, then the imputed onset date will be the latest of the following non-missing dates:
 - Date of first dose of study drug
 - Surrogate onset date

If the imputed onset date is after the adverse event end date, the imputed onset date will be the same as the adverse event end date.

7 **REVISION AND RATIONALE**

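### SAP 5.4.1 ignores the AE end date when the onset date is incomplete, so an event recorded as over before dosing can be counted as treatment-emergent (minor)

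*SAP*

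**What the plan says.** Both documents tie treatment emergence to dosing. SAP 5.4.1: "TEAE is defined as an AE observed after ASP5354 administration and up to the follow-up period (up to Day 10"). Protocol 9.5.1: "A TEAE is defined as an AE observed after administration of the IP and up to the follow-up period". SAP 6.5.1 repeats the protocol's definition.

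SAP 5.4.1 then gives two rules for incomplete onset dates:

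- Completely missing: "Any AEs with onset dates completely missing will be considered TEAEs in summaries unless the investigator has noted on the CRF the event began" before treatment.
- Partially missing: "AEs with partially missing onset dates will be assumed TEAEs unless the available portion of the date indicates" an onset strictly before study medication.

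Neither rule mentions the end date. SAP 5.4.1 also has check boxes for onset before or after study drug, but these apply to an AE that occurs on Day 1.

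SAP 6.10.2 does use the end date when it imputes onset: "If the imputed onset date is after the adverse event end date, the imputed onset date will be the same" as that end date. It gives steps for a year-only onset and a month-and-year onset. It announces a rule for missing onsets as well, but gives no steps for them.

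Pre-dose events do enter the database. Protocol 7.3.1: "AE collection begins after the signing of the ICF". The Schedule of Assessments (Protocol Table 1) places screening on Day -28 to -1, with AE assessment at that visit.

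**The concern.** Assuming treatment emergence when timing is uncertain is normal and sensible. It resolves doubt against the drug. With a single dose, however, a recorded end before dosing removes the doubt, because an event that was over before the dose also began before it. The partial-date rule still counts that event.

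Three things follow. The TEAE tables can include events that fail the SAP's own definition. The dataset can hold an AE flagged treatment-emergent whose imputed onset and recorded end are both pre-dose. And an investigator's note that the event began before treatment is honoured, outside the Day 1 check boxes, only when the onset date is completely missing. Someone who also knows the month or year has given more information but loses the exception.

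TEAEs are a secondary endpoint and are tabulated by dose group. A group may hold as few as 3 subjects if a dose is stopped at the first committee review.

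**Working it through.** The plan states no figure to reproduce, so the check applies the two SAP sections literally to the same events. The dates are assumed for illustration.

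**Main example.** Dosing 20 Jun 2021, onset known only as June 2021, recorded end 10 Jun 2021.

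1. SAP 5.4.1: the known part of the onset is June 2021 and dosing is in June 2021. The known part is not strictly before dosing, so the event is a TEAE.
2. SAP 6.10.2: the surrogate onset is 1 Jun. The onset month is the dosing month, so the imputed onset is the later of 20 Jun and 1 Jun, which is 20 Jun. That is after the recorded end, so it is reset to 10 Jun.
3. 20 Jun − 10 Jun = 10 days before dosing. The two sections disagree.

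**Other cases.**

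| Dosing | Known onset | Recorded end | SAP 5.4.1 | Onset under SAP 6.10.2 | Result |
|---|---|---|---|---|---|
| 20 Jun 2021 | 2021 | 10 Jun 2021 | TEAE | later of 20 Jun and 1 Jan = 20 Jun, capped to 10 Jun | conflict |
| 20 Jun 2021 | May 2021 | 10 Jun 2021 | not TEAE | 1 May | agree |
| 20 Jun 2021 | June 2021 | 25 Jun 2021 | TEAE | 20 Jun | agree |
| 20 Jun 2021 | none, no CRF note | 10 Jun 2021 | TEAE | no steps given | conflicts with the TEAE definition only |
| 15 Jan 2021 | 2020 | 20 Jan 2021 | not TEAE | later of 15 Jan 2021 and 1 Jan 2020 = 15 Jan 2021 | sections differ the other way |

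The last row shows that 6.10.2 cannot simply be put in charge of TEAE status. It moves a year-only onset from an earlier year up to the dosing date.

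**How general the conflict is.** Take each dosing day of one year (365) and every pair of onset and end days in the 28 days before dosing, with onset no later than end: 28 × 29 / 2 = 406 pairs per dosing day, and 365 × 406 = 148,190 pairs. All are pre-dose events.

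- Onset day missing: 5.4.1 labels 55,622 as TEAEs; 55,622 / 148,190 = 37.5%.
- Only the onset year known: 140,476 / 148,190 = 94.8%.

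In every pair so labelled, the 6.10.2 onset is before dosing. These shares weight all pairs equally and apply only to events that start and end in screening and have an incomplete onset. They are not expected error rates.

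**Effect on a table.** One extra subject with a TEAE changes a group's rate by 100 / n points: 100 / 15 = 6.7 and 100 / 3 = 33.3. SAP 6.5.1 counts subjects, so these are maxima. The overall rate moves only if the subject has no other TEAE. A row for one preferred term moves only if the subject does not already count in that row.

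**The case against.** The best defence is that the headline definition already excludes an event that ended before dosing, so the missing-date rules are only presumptions for events whose timing is unknown. A programmer who derives the flag from the 6.10.2 date would also get the main example right. This is a fair account of the likely intent, but it does not settle the text. SAP 5.4.1 states its own rule with its own exceptions, nothing says that 6.10.2 governs, and 6.10.2 goes wrong in the last row of the table.

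The limits on scale do stand. The error needs an AE that began and ended before dosing, an incomplete onset, a usable end date, and a known onset month or year not strictly before dosing. AEs are collected prospectively, eCRF entry is expected within 5 days of the visit and is checked against source (Protocol 10.1), and all AE data are listed. A pre-dose end date would be visible to a reader of the listings.

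Three stronger readings are tempting, and the documents do not support them:

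- A reader might infer that completely missing onsets also contradict 6.10.2. They do not, because no imputed date is defined for them. The CRF-note exception may also remove some of these events.
- A reader might take the share of screening days that fall in the dosing month as the error rate. For a 28-day screening period and a dosing day uniform over a 30-day month, that share is 434 / 840 = 52%. It shows only when a month-only onset is ambiguous. It does not require the event to have ended before dosing, or the date to be incomplete.
- A reader might infer that dose selection or the main result is at risk. The primary endpoint is visualization, no safety hypothesis is tested, and the committee criteria named in SAP 2.2 are visualization and fluorescence intensity, although its remit over all collected data is open-ended.

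**Conclusion.** The point holds as a minor defect. For month-and-year or year-only onsets, SAP 5.4.1 can flag as treatment-emergent an event recorded as over before dosing, against the TEAE definition and against the end-date cap in 6.10.2. For completely missing onsets without a CRF note, only the definition is contradicted.

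The direction is over-counting. The size is at most 6.7 points per event in a group of 15 and 33.3 in a group of 3. The conclusion rests on a literal reading of 5.4.1. How often it would occur cannot be worked out from the documents. It is probably seldom, and the effect stays within descriptive safety tables.

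**What to change.** Add one exception to both missing-date rules in SAP 5.4.1, for example: *An AE whose onset date is partly or wholly missing is not treatment-emergent if its recorded end date is before the date of ASP5354 administration, or if the investigator has recorded on the CRF that it started before treatment.* Keep the rest of the conservative rule, so that an event ending on or after the dosing date is classified as now unless such a note exists. State that 5.4.1 governs TEAE status, and cross-refer to it from 6.10.2.

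The cost is one clause, one cross-reference and one extra condition in the TEAE derivation. It uses end dates and investigator notes already provided for and needs no new data collection.
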